Filtration In the Neuropathy of End-Stage kidney disease Symptom Evolution (FINESSE) Statistical Analysis Plan

[figure not shown]
[name], [name], [name], [name], [name], [name], [name], [name], [name], [name], [name]

Trial Registration: ACTRN12609000615280

Statistical analysis plan 1, version 2, 2/1/19

Based on protocol 1, version 4, 21 August 2013, X13-0300 (formerly X09-0172)

Signatures

Person writing SAP: [name]

2/1/19
Date

[name] Digitally signed by [name]
Date: 2019.01.02 16:56:23 +11'00'

Senior statistician responsible: [name] Date

Chief investigator: [name]

2/1/19
Date

FINESSE study statistical analysis plan summary of changes from version 1 to 2

Page/section	Changed text	Comments/Rationale
2.3 Sample size	“moderately severe to severe” changed to “moderate to severe”	Correction of typographical error in version 1
4.4 Baseline characteristics 5.1 Outcome definitions Appendix 1	Neuropathy assessment “total neuropathy score” changed to “modified total neuropathy score”	Adjective added to accurately represent the tool as specified in the protocol
2.2 Randomisation 5.2 Analysis methods	Maximum score of TNS changed from 32 to 28. As the modified TNS does not include vibration, the maximum score is 28.	The study protocol specifies the use of a modified Total Neuropathy Score. The specific modification is the exclusion of the vibration domain. The consequence is that the total possible score in FINESSE is 28.
5.1 Exploratory analyses	Physical examination (pin sensitivity, strength, tendon reflexes)	“Vibration” removed in accordance with use of modified TNS as described above
5.1 Exploratory analyses	Repeat primary and appropriate secondary analyses using original (not modified) Total Neuropathy Score.	Addition of sensitivity testing using original Total Neuropathy Score
Appendix 1	Vibration row removed from table Interpretation severe neuropathy changed from “25-32” to “25-28”	As above

1.1 Background and Rationale

Uraemic neuropathy is a common complication of end stage kidney disease (ESKD), affecting 60-100% of patients receiving dialysis therapy[1-3]. It is a sensorimotor progressive polyneuropathy causing pain, loss of sensation, weakness and muscle wasting, and leading to disability and poor quality of life. The pathophysiology is believed to be the result of accumulated metabolic toxins. A small cross-sectional study suggested improved nerve excitability in patients undergoing haemodiafiltration, which provides greater clearance of small and middle molecules, compared to high flux standard haemodialysis[4]. No previous randomised trials have reported the effect of haemodiafiltration versus high flux haemodialysis on neuropathy[5].

1.2 Objective

We aimed to determine the effect of haemodiafiltration compared to high flux standard haemodialysis on the occurrence and progression of uraemic neuropathy in recipients of maintenance haemodialysis therapy.

2 Study Methods

2.1 Trial Design

The Filtration In the Neuropathy of End-Stage kidney disease Symptom Evolution (FINESSE) study is a parallel 2-arm, multi-centre, open-label, randomised controlled trial of haemodiafiltration versus standard high flux haemodialysis for uraemic neuropathy in patients with ESKD. All participants received routine medical care and monitoring including the recommendation of a multivitamin[6].

2.2 Randomization

Participants were randomised to receive either haemodiafiltration or standard high flux haemodialysis. Participants were randomised in a 1:1 fashion with stratification by baseline neuropathy score. Strata 1 was defined as TNS score 0-8 (no to minor neuropathy) and strata 2 as TNS score 9-28 (moderate to severe neuropathy). The allocation sequence was based on blocks of 4 and generated centrally by an independent statistician who had no other involvement in the study. To ensure allocation concealment, randomisation was performed by an independent university employee based in a physically separate site with no other involvement in the study. The randomisation schedule was known only to the independent university employee, the generating statistician and the unblinded statistician.

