2.3 Sample Size

Total Neuropathy Score was selected to measure the primary endpoint as it met the requirements for neuropathy assessment as articulated in the 2005 Consensus Statement[7]. However, at the time the study was designed, *there were no available results for Total Neuropathy Score assessments in dialysis patients*. Accordingly power calculations were made using information on Neuropathy Symptom Score grades and sural nerve conduction values that were available when the study was designed[3, 8, 9]. Using assumptions based on those studies FINESSE was calculated as having more than 90% power to detect a reduction in moderate to severe neuropathy from 80% in the control arm to 48% prevalence in the treatment arm (absolute difference of 32%) with a sample size of 120 (with $\alpha=0.05$), including an allowance for 20% combined drop-out and loss to follow-up

(n=96 in the final analysis). We also calculated that with 90% power (with $\alpha=0.05$) the study could detect an absolute difference of 2.6mcV in the mean response of sural nerve sensory amplitudes between the treatment groups (assuming a standard deviation of 3.9).

Since developing the original protocol, studies have been conducted that provide data on the Total Neuropathy Score from an external cohort of dialysis patients ([name], personal communication). In 49 dialysis patients, the mean TNS was 9.2 (SD: 7.8) with 42% (20/48) having a TNS score of 17-32 (moderate to severe neuropathy). Using these assumptions, FINESSE has 90% power to detect a mean difference of 5.2 in TNS between treatment arms at the end of the study and 80% power to detect a mean difference of 4.5.

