3.1 Confidence intervals and p values

All tests are two-sided and the nominal level of alpha will be 5%. P-values will not be adjusted for multiplicity.

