5.1 Outcome Definitions

Primary Outcome

The primary end-point for this study is the difference in the mean change in modified total neuropathy score (TNS) from baseline between the two groups.

Mean changes from baseline will be analysed using a restricted maximum likelihood (REML)-based repeated measures approach (MRMM). Analyses will include the fixed, categorical effects of treatment, visit (unstructured), and treatment-by-visit interaction, as well as the continuous, fixed covariates of baseline score and baseline score-by-visit interaction. We will test a range of covariance structures (autoregressive(1), heterogeneous autoregressive(1), unstructured, compound symmetry structure) and select the structure with

the lowest AIC (best fit). The Kenward-Roger approximation will be used to estimate denominator degrees of freedom. Analyses will be implemented using SAS/Stat 14.2.

The primary comparison will be the average of the contrast between treatment groups across all time points in the study, with each observed time-point weighted equally.

Secondary Outcomes

These will follow the same plan approach for the primary outcome (MRMM), with different comparisons and distributions for the outcomes as appropriate.

1) Neuropathy outcomes. Analyses will include:

- a) Difference between groups in mean change from baseline in modified TNS at years 1, 2, 3, 4 with the same method as the primary analysis
- b) Difference between treatment groups in proportion of participants with modified TNS 0-8 (no or minor neuropathy) overall (time-points weighted equally) and at 1, 2, 3 and 4 years, using a generalised linear mixed model with a binomial distribution and a logit link.¹
- c) Difference between groups in mean change from baseline in NSS overall (as per main outcome), and at 1, 2, 3 and 4 years with the same method as the primary analysis.
- d) Difference between treatment groups in proportion of participants with no or asymptomatic neuropathy on NSS (NSS stage 0-1) overall, and at 1, 2, 3 and 4 years using a generalised linear mixed model with a binomial distribution and a logit link .
- e) Difference between treatment groups in change in sural nerve sensory amplitude (mV) from baseline overall, and at 1, 2, 3 and 4 years with the same method as the primary analysis.

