5.2. Secondary/SAEs outcomes

A summary of each secondary or safety endpoint will be provided. Continuous outcomes will be summarised by their mean (SD), while binary outcomes will be summarised by percentages.

Continuous: All continuous secondary endpoints without repeated measurements will be analysed using linear regression adjusted with its baseline counterpart. This applies to the exploratory analyses

Continuous repeated measurements: All secondary outcomes repeatedly measured over time (Secondary outcomes 1a, 1c, 1e) will be modelled using a Linear Mixed model including random intercept, randomisation and time categories as per the analysis of the main outcome (5.1). The Linear Mixed model will be formulated to use Direct Likelihood, which will allow for data that is missing at random.

Binary repeated measurement: will be analysed using generalised linear mixed model with a logit link and a binary distribution (logistic regression), for Secondary outcomes 1b and 1d.

Count: Count secondary endpoints, such as number of reported access-related AEs, will be modelled using a Poisson regression model, and a negative binomial model if there is overdispersion (>1.3). This will apply for secondary outcomes 2b, 2c, 2e, 2f, 2g, 2h.

Survival time: Survival curves and estimated median survival time will be generated according to the Kaplan-Meier method. Log-rank test will be used to assess the difference between the two survival curves by secondary endpoint. The hazard ratio between two treatments will be estimated with a Cox Proportional Hazards model if the PH assumption is met. This will apply for Secondary outcomes 2a and 2d.

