Composite Rank Score: A rank-based procedure combining mortality and functional neuropathy score will be used (Secondary outcome 4). Patients who die before the 48 month follow-up will be ranked from lowest (poorest outcome) to highest on their survival time (less survival time=lower rank). Then, those who are alive at the final follow-up with a TNS will be ranked from least to most favourable change in TNS from baseline (TNS follow-up – TNS baseline) . If participants are alive but do not have a valid TNS then they will be censored (Shortest Survival < Longest Survival < Lowest TNS change < Highest TNS change). Ranks between treatment groups will be compared with a log-rank test, and hazard ratio (with 95% confidence intervals) will be estimated with Cox proportional hazards regression. The main assumption underlying the composite ranking is that death at any time is worse than the greatest increase in TNS.

Sensitivity test for missing data in the main outcome: A sensitivity analysis of the missing at random assumption in the main outcome will be made with a delta-adjustment tipping point analysis. If a significant difference is found between the groups we will use a marginal delta adjustment method with a tipping point. We will impute missing visits (using a non-monotone MCMC method), then add a constant (delta) to the imputed data until the difference is no longer significant ($p>0.05$). If the value of delta required to overturn significant results is implausible then we will consider the results to be robust.

Further analyses: Further analyses for the cohort phase of the study will be subject to a separate report when data is available.

Serious adverse event outcomes:

Serious adverse event outcomes will be independently categorized by two authors into the following groups (as defined above):

- Access failure
- Septicaemia
- Cardiovascular event
- Surgery for carpal tunnel syndrome
- Parathyroidectomy surgery
- Fractures requiring or occurring during a hospital admission
- Other

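### The ranked composite, time-to-event and count analyses ignore the baseline TNS stratum used at randomisation; the cost is some power, chiefly for the composite, and no bias

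*SAP*

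**What the plan says.** Section 2.2 sets the design: "Participants were randomised in a 1:1 fashion with stratification by baseline neuropathy score". It continues: "Strata 1 was defined as TNS score 0-8 (no to minor neuropathy) and strata 2 as TNS score 9-28 (moderate to severe neuropathy"). Allocation was blocked: "The allocation sequence was based on blocks of 4 and generated centrally by an independent statistician".

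The analyses treat this factor differently:

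- **Primary outcome (5.1).** The model has continuous baseline score and its interaction with visit. For TNS this covers the stratifier more finely than the two-level split.
- **Repeated neuropathy outcomes (1b-1e).** Section 5.1 says the secondary outcomes follow the primary approach, for example "Difference between groups in mean change from baseline in NSS overall (as per main outcome"). It does not say whether the baseline score is then baseline TNS or the outcome's own baseline. The section on secondary and SAE outcomes describes the continuous models again, listing a random intercept, randomisation and time, with neither baseline nor stratum.
- **Time to event (2a, 2d).** "Log-rank test will be used to assess the difference between the two survival curves by secondary endpoint". A Cox model follows. No covariate or stratum is named.
- **Counts (2b, 2c, 2e-2h).** Poisson or negative binomial. No covariate or stratum is named.
- **Ranked composite (4).** "Ranks between treatment groups will be compared with a log-rank test", with a Cox hazard ratio. No covariate or stratum is named.

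Elsewhere among the analyses the stratum appears only as the first subgroup in section 5.2.

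**The concern.** When allocation is balanced on a factor that predicts the outcome, an analysis that ignores the factor does not use the balance it has paid for. In a linear model the factor's variance stays in the error term. In a log-rank or Cox analysis the treatment estimate is pulled towards no effect.

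The composite is the clearest case because the link with the stratum is built into the outcome. Survivors are ranked on follow-up TNS minus baseline TNS, on a scale bounded at 0 and 28. Room to improve therefore differs by stratum, and regression to the mean acts in the same direction. The primary model deals with this through its baseline terms; the composite, which uses the same change score, does not. With about 96 participants expected in the final analysis, several points of power are worth keeping.

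**Working it through.** **1. The plan's own figures.** These reproduce with 48 per arm, two-sided 5%, power = Φ(δ/(SD·√(2/48)) − 1.96):

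- TNS 4.5, SD 7.8: 4.5/(7.8 × 0.2041) = 2.83; power 80.7% (plan: 80%).
- Sural amplitude 2.6, SD 3.9: 2.6/(3.9 × 0.2041) = 3.27; power 90.4% (plan: 90%).
- 80% versus 48%: power 91.7% (plan: more than 90%).
- Dropout: 96/(1 − 0.20) = 120.

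None of these uses the stratum, so the point does not disturb the sample size.

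**2. Ranked composite.** Inputs from section 2.3: 120 randomised, TNS mean 9.2 and SD 7.8 (clipped here to 0-28), effect 4.5 points. From section 2.2: strata 0-8 and 9-28, blocks of 4. Assumed, because the SAP gives no values: baseline-to-follow-up correlation ρ of 0.5, 0.7 or 0.85; 15% or 30% deaths; 20% of survivors without a TNS (censored). A fall in TNS is taken as favourable. There were 1000 runs per scenario.

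Before clipping, and with equal SDs, baseline explains (1 − ρ)/2 of the variance of change: 25%, 15% and 7.5%. The two-level stratum captures part of that, about 18% down to 6% in the simulated data under no effect.

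| Deaths | ρ | Power, unstratified | Power, stratified | Gain (points) |
|---|---|---|---|---|
| 15% | 0.5 | 43.5% | 55.0% | 11.5 |
| 15% | 0.7 | 65.0% | 71.0% | 6.0 |
| 15% | 0.85 | 91.7% | 93.7% | 2.0 |
| 30% | 0.5 | 28.6% | 34.1% | 5.5 |
| 30% | 0.7 | 46.1% | 51.3% | 5.2 |
| 30% | 0.85 | 73.9% | 75.6% | 1.7 |

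An independent repeat gave gains of about 2 to 10 points, again positive in all six scenarios. Under no effect, rejection was 3.7-5.5% unstratified and 4.1-6.3% stratified. Simulation error is about ±1.4 points (1.96 × √(0.05 × 0.95/1000)), so no clear difference in type I error is shown.

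**3. Cox model for an ordinary event.** n = 120, stratified blocks of 4, four years of follow-up, true treatment hazard ratio 0.5, about 31 to 35 events, 2500 runs. The stratum's hazard ratio is assumed.

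| Stratum HR | Reported SE, without / with stratum | Power, without / with stratum |
|---|---|---|
| 1 | 0.388 / 0.388 | 43.9% / 44.4% |
| 2 | 0.380 / 0.380 | 44.8% / 46.8% |
| 4 | 0.361 / 0.361 | 43.9% / 49.9% |

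The reported standard error does not move; the estimate does. At stratum HR 4 the mean log hazard ratio is −0.655 without the stratum and −0.704 with it, that is exp(−0.655) = 0.52 against exp(−0.704) = 0.49. Under no treatment effect at stratum HR 4, rejection is 3.4% without the stratum and 5.3% with it.

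**4. NSS and sural amplitude (1c, 1e).** Three readings are possible:

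- *Baseline TNS is the covariate:* the stratifier is already covered.
- *The outcome's own baseline is the covariate:* in simulations with n = 96, adding the stratum changed the SE by about 0-2% in five of six scenarios (for example 0.1477 to 0.1454). In the most extreme it fell by 7% (0.1634 to 0.1513).
- *No baseline covariate, as the second description could be read:* the SE is too large by 1/√(1 − R²) − 1. For an assumed R² of 5%, 10% or 20% that is 2.6%, 5.4% or 11.8%. The true size of the test, 2(1 − Φ(1.96/√(1 − R²))), is 4.4%, 3.9% or 2.8%.

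**The case against.** The strongest reply is that this is a small and safe-sided matter. Stratified allocation balances the 8-versus-28-point difference in room to improve between the arms, so the composite comparison is not biased. The primary analysis adjusts for continuous baseline TNS. No power is claimed for the safety outcomes or the composite. Nothing in the SAP says that baseline TNS predicts access failure, septicaemia, parathyroidectomy or fracture; for these the gain may be nil. All of this stands, and it limits the point to efficiency.

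It could also be said that section 5.1 sends every secondary outcome to the primary approach, baseline covariate included. That is fair for 1b-1e. It does not rescue outcomes 2 and 4, for which the later section sets out separate methods with no covariate.

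Three stronger readings are tempting but unsupported:

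- *That standard errors are too large throughout.* This is a linear-model result. In the Cox simulation the reported SE was the same with and without the stratum, and the R² formula was not derived for log-rank, count or logistic models.
- *That the gain from stratifying is lost.* Balance by design remains, and the primary model keeps the precision.
- *That NSS and sural amplitude are unadjusted.* The text in 5.1 carries a baseline score over to them; what is unclear is which one.

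Nor is the change entirely free. In Cox and logistic models, conditioning on the stratum alters the quantity estimated, from a marginal to a within-stratum ratio.

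**Conclusion.** The point holds as one of efficiency and specification. The composite, the log-rank and Cox analyses and the count models omit the randomisation stratum and baseline TNS. For the composite the loss is about 2 to 12 points of power for a 4.5-point effect. This is conditional on the assumed correlations, death rates and 20% missing TNS; the gain is largest where baseline and follow-up correlate least.

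For 2a and 2d it depends on how strongly the stratum predicts the event, which the SAP does not state: under one point if not at all, about 2 points at a hazard ratio of 2, about 6 at a hazard ratio of 4. The count models were not simulated. For 1c and 1e the gain is usually 0-2% in the SE, provided a baseline covariate is kept.

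The primary result and the sample size are unaffected, and the direction of error is conservative where any is visible. The change is worth making before analysis, chiefly for outcome 4.

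**What to change.** In the section on secondary and SAE outcomes:

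1. For outcomes 4, 2a and 2d, specify a log-rank test and Cox model stratified by the randomisation stratum (modified TNS 0-8 versus 9-28, as recorded at randomisation). The composite ranking itself need not change, because a stratified log-rank test uses only the order within each stratum.
2. For the count models, add the stratum as a fixed effect where event numbers allow. State in advance that it is dropped for very rare events, which may apply to 2f and 2g.
3. For 1b-1e, reconcile the model described in 5.1 with the later description, so that the baseline score covariate is plainly retained. State whose baseline it is, and add the stratum or baseline TNS wherever that covariate is not baseline TNS.

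The cost is a few sentences of SAP text and one term in each program. The stratum was needed to randomise, so it should be known for everyone. The report should say that hazard ratios and odds ratios are conditional on the stratum. Writing this in before the analysis also avoids choosing covariates after seeing results.

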2.3 Sample Size

Total Neuropathy Score was selected to measure the primary endpoint as it met the requirements for neuropathy assessment as articulated in the 2005 Consensus Statement[7]. However, at the time the study was designed, *there were no available results for Total Neuropathy Score assessments in dialysis patients*. Accordingly power calculations were made using information on Neuropathy Symptom Score grades and sural nerve conduction values that were available when the study was designed[3, 8, 9]. Using assumptions based on those studies FINESSE was calculated as having more than 90% power to detect a reduction in moderate to severe neuropathy from 80% in the control arm to 48% prevalence in the treatment arm (absolute difference of 32%) with a sample size of 120 (with $\alpha=0.05$), including an allowance for 20% combined drop-out and loss to follow-up

(n=96 in the final analysis). We also calculated that with 90% power (with $\alpha=0.05$) the study could detect an absolute difference of 2.6mcV in the mean response of sural nerve sensory amplitudes between the treatment groups (assuming a standard deviation of 3.9).

Since developing the original protocol, studies have been conducted that provide data on the Total Neuropathy Score from an external cohort of dialysis patients ([name], personal communication). In 49 dialysis patients, the mean TNS was 9.2 (SD: 7.8) with 42% (20/48) having a TNS score of 17-32 (moderate to severe neuropathy). Using these assumptions, FINESSE has 90% power to detect a mean difference of 5.2 in TNS between treatment arms at the end of the study and 80% power to detect a mean difference of 4.5.

2.4 Timing of Outcome Assessments

Data on neuropathy outcomes were collected at baseline, 1, 2, 3 and 4 years after randomization. Data on all other study endpoints were collected at baseline and 6 monthly follow-up visits until 4 years from randomization. Assessments may be conducted at other time points for participant or assessor reasons. If this occurs, the results will be allocated to the nearest unmeasured outcome assessment time point.

2.4.1. Data Linkage

Data linkage offers a means of ascertaining differences in mortality and late clinical events while minimising the trial demands on participants and sites. Participants consented to data linkage beyond the 48 month duration of the study to the Australia and New Zealand Dialysis and Transplant Registry (ANZDATA) to gather information on vital status and technique survival. The ANZDATA information will establish the durability of each intervention and medium-term effects on participant survival.

Participants also consented to long term follow-up through data linkage to the Department of Human Services Medicare Benefits Schedule (MBS) and Pharmaceutical Benefits Scheme (PBS).

The analysis of linked data and long-term follow-up outcomes will be the subject of a separate Statistical Analysis Plan.

3 Statistical Principles

